Institutional Review Board
Approved *[name]*
Date *12/14/17*

RECEIVED

JUL 03 2018

LLUH Responsible
Research Services

Institutional Review Board CHANGE REQUEST FORM

RESEARCH PROTECTION PROGRAMS | LOMA LINDA UNIVERSITY | Office of Research Affairs
[name] [contact] (voice) / [contact] (fax)/e-mail: [contact]

Principal Investigator: [name]

Department: Psychology

Protocol Title: Mindful awareness for parenting stress (MAPS) project for parents of children with developmental delays

IRB #: 5110264

Approval End Date: Aug 20, 2018

Current Stipulations: N/A

I. This Change Request is a result of: (check all that apply)

- Initiated by Sponsor.
- Initiated by local (LLU) Investigator.
- Result of Adverse Event;
re: AE report submitted: ("Unique Identifier")
- Protocol change was necessary to eliminate apparent immediate hazards to subject(s).

II. Protocol Change(s):

- a. Briefly summarize this Change Report, using the preferred wording to appear in the IRB's approval letter.
(This is also the only description appearing in future protocol profiles.)

We are submitting changes to our phone screen, consent form, and questionnaire measures to be consistent with our recently awarded NIH grant (LLeRA 2170159) which falls under this IRB. More specifically, for the phone screen, we are going to ask parents whether their child has an autism spectrum diagnosis, administer the Parenting Stress Index-Short Form 4th Edition instead of the Perceived Stress Scale during the phone screen, and screen for exclusionary criteria. A very similar phone screen was approved for another study of mine (HS 5170325) and these questions have worked very well.

With regard to the consent form changes, we have updated the our previous consent form from the MAPS project to reflect the revised aims and procedures for the NIH grant. We have included a clean copy of our new consent form (title is Stress-reduction techniques for effective parenting skills (STEPS) project), our previous MAPS consent with the track changes, as well as a clean copy of the approved MAPS consent form in order to make the changes clear.

With regard to questionnaires, for the NIH grant we have added a few parent questionnaires. More specifically, we have included a revised version of the Parenting Stress Index (we are now using the 4th edition instead of the 3rd edition that we used on MAPS), the Social Communication Questionnaire, Attachment Q-Sort questionnaire, Beck Anxiety Inventory, Behavioral Inhibition Questionnaire, Preschool Anxiety Questionnaire, Repetitive Behavior Scale-Revised, Family Resource Scale, Parenting Scale, and Parental Flooding Scale. We have also added one teacher-report questionnaire, the Preschool Anxiety Questionnaire-teacher report version. All of these measures are psychometrically sound and have been frequently used with families of young children with developmental delays and Autism Spectrum Disorder.

b. Classification of significant change(s):

- SAFETY

1a. List any change(s) in monitoring (number each change):

1b. If any item(s) listed above DECREASE monitoring, explain why subject safety will NOT be adversely affected.

- PROCEDURES

2a. List any change(s) in subject-related intervention (number each change): None
2b. What is the scientific justification for item(s) above, and explain how risk to subjects is affected:

There is no additional risk to subjects. The changes are scientifically justified because the revised changes to the phone screen, consent, and questionnaires will more accurately identify the families eligible for this study (phone screen), provide more accurate information to participants about what the study will entail (consent), add additional psychometrically sound measures to assess the constructs of interest, and is in line with the NIH funded proposal.

SUBJECTS

3a. List any change(s) that remove exclusion criteria or broaden inclusion criteria (number each change): The study will now focus on children with Autism Spectrum Disorder specifically, rather than children with developmental delays more broadly.

3b. Justify any item(s) above that remove safety exclusion or modifies fairness in subject selection: This is what was approved by NIH for this project.

ADMINISTRATIVE

4a. Change study title of IRB approval to the following: Stress-reduction techniques for effective parenting skills (STEPS) project

4b. If study personnel will be changed, use the "Request to Change IRB Study Personnel" form.

4c. If sponsor has changed, name of sponsor is:

If yes: "Great! Before I go over all of the study details, I would like to point out that this particular intervention is for parents of children with ASD. Is your child currently diagnosed with an autism spectrum disorder?"

Complete Section I

If yes:

"If you have a few minutes, I'd like to tell you a little more about this study. Is now a good time?"

If no:

Explain that we're only recruiting children with an ASD diagnosis at this time so they will not be eligible for the study but we plan on having more groups for parents of children with developmental delays. Ask if they would like to be placed on the waitlist to be contacted for the next study. Thank them for reaching out and for taking the time to hear about the study. After hanging up, add family to the waitlist and input all of the necessary info.

2. Brief Summary of the Intervention:

"The STEPS Project is an intervention study taking place at Loma Linda University in collaboration with Cal State Fullerton for parents of children with autism spectrum disorder. It was put in place to provide support for parents and to reduce parenting stress. Our hope is that this experience will help reduce your parenting stress, enable you to feel more confident as a parent, reduce concerns you have about your child, and in turn, improve your child's behavior.

As a part of this study, you would participate in one of two parent interventions. One intervention focuses on mindful awareness and the other is an educational parent support group. Both groups run for 8 weeks and have one 6-hour weekend event during week 6. If you choose to enroll in the program, it will be very important for you to attend all 8 intervention sessions and the weekend event. Childcare will be provided. Groups will be either Monday or Wednesday night and both will begin mid-January 2019 and end in March 2019. You will be randomly assigned to a group, like the flip of a coin. We will let you know which group you will be assigned to after your first lab assessment.

As I said, we are offering these interventions as part of a research study and therefore, in order to determine how effective the treatments are, we are asking that families participate in five lab visits for assessments. There will be two before the group begins, one immediately after the group is completed, one 6 months after the group is done, and one 12 months after the group is done.

- If yes: "Great! I will add your information to our waitlist and we will reach out as soon as we begin recruitment for the next study." ***Confirm name, two contact numbers, and an email address. Also note if child has an ASD diagnosis and is Spanish-speaking or not. Fill in all the columns on the waitlist with info already collected***

- If no: "Thank you for taking the time to reach out and hear more about the STEPS Project. Have a great day."

***If the child is too old to participate in this study, inform the parent that we are currently only recruiting children between the ages of 3 and 6. Thank them for their time and for expressing interest in the study.

*****MAKE SURE TO GET PC MIDDLE NAME**

Because suicidality will be screened for later in the call, you need to get the parent's current location. Ask the parent, "Where are you now?" and try to obtain a physical address.

Make sure to get 2 phone numbers whenever possible (even if one is a relative).

5. Guidelines for section III:

When asking about diagnosis and details, be sensitive to the parent's educational level as well as comfort level.

If they don't seem to understand some of the terminology (e.g. diagnosis), use the suggested alternatives to phrase the questions.

6. Guidelines for section IV:

Ask the parent the PSI-4 Short Form questions provided on the phone screen. As you go thru the questions, make sure to enter answers on the Excel sheet to get a total score. As you type in responses, make sure to use the right scale by checking the scoring keys on the right. If the parent does not reach the clinical cut off (score of 110), they will not be eligible for the study.

If eligible: ***Continue on to Section V***

If not eligible: "Unfortunately, for this study we are only including families with a certain level of parenting stress. Based on your responses, you do not meet criteria at this time. We will have more parenting groups coming up that you may still be eligible for. Would you like to be added to that waitlist?"

If yes: Add to waitlist, make sure to collect all the information that you have not already gotten in this screen

If no: Thank them for their time and for reaching out.

Parents may be sensitive in discussing their stress levels. If necessary, reassure them that you ask the same questions of every parent and that many of these feelings are common.

7. Guidelines for section V:

Ask for specifics on any services the parent has received or is currently receiving.

If the parent is currently receiving services for himself/herself, inform him/her that because we are looking at the impact of this particular intervention on families we are asking that parents not receive any other psychotherapy services for themselves while the intervention is taking place. This is to ensure that any effects we observe are a result of our intervention and not other psychotherapy services. However, we will take their information and speak with the principle investigator for a case-by-case decision regarding their current services. Children can continue to receive behavioral and psychotherapy services.

8. Guidelines for section VI:

Ask these questions to assess parent / child exclusionary criteria.

Child Exclusionary Criteria Questions:

If the child meets an exclusion criterion, inform him/her that we will be unable to accept them for the study at this time. Explain why the format of the study would make it difficult for their child to participate. Sympathize with their disappointment and ask if they would be interested in other referrals. If the parent expresses interest, let them know that you will inform [name] and she will call within a week to discuss their situation and to offer useful resources.

If you are unsure if a child meets an exclusion criterion, notify the parent of your concern, and let them know that we will need to call them back later for more information.
(Continue with screen)

Parent Exclusionary Criteria Questions:

When asking the parent these questions, be aware that they may be sensitive topics for some individuals. Take notes as necessary and write down details/clarifications that parents provide for these questions on the phone screen document.

If parent endorses drug use / psychosis items and / or you are not sure if they should be excluded for drug use:

Inform the parent that they may not meet some of the study requirements. Ask if they are okay with [name] calling within the next week to follow up for more details and to discuss their eligibility for the study. She will also be able to provide some potentially useful resources if they are interested. (Continue with phone screen)

If parent endorses suicidality items:

- Endorses first question of letter "I": passive ideation
 - Complete the top section of the Suicide Risk Assessment Form (Assessment of Suicidal Thoughts)
 - Let the parent know that [name] will follow up within the next 24 hours
- Endorses "I" and "1": Strong Intent
 - Complete an in depth risk assessment. Fill out the entire Suicide Risk Assessment Form (1 page)
 - "I am going to ask [name] to call you within 24 hours. How confident are you that you can keep yourself safe until then?"
 - Confident that they will not harm themselves: Reassure that they will be getting a call from [name] within the 24 hour time frame.
 - Not able to keep themselves safe: go thru procedure for 'imminent risk' as seen below
- Endorses "I", "1" and "2": Imminent Risk
 - Complete an in depth risk assessment. Fill out the entire Suicide Risk Assessment Form

- o Suggest to the parent that they seek help quickly.
- o Ask if they are willing to go to the hospital voluntarily.
 - Yes: "Do you have a way to get there?" (i.e. family or friend to drive them)
 - No: call 911 immediately
- Endorses "c" under question "K" –
 - o Complete an in depth risk assessment. Fill out the entire Suicide Risk Assessment Form.
 - Will either qualify as strong intent or imminent risk
 - Respond accordingly using guide seen above.
- After any level of endorsement for suicidality, call [name] immediately following the phone screen: [name]

9. Guidelines for section VII:

Ask the family for the name, address and phone number of AT LEAST one person who will always know how to contact them. This is extremely important, as we may not have contact with these families again for a few months.

Use this section to give parents control of the conversation and to talk briefly about their children. Give them the opportunity to voice any concerns they may have and answer their questions as best as you can (see point 10).

Make note of any possible exclusionary concerns (and mention them to the parent, following the above guidelines).

If you don't know the answer to any questions they have, write the question down and tell the parent you will have the project director call them back.

10. ALWAYS complete Section VII immediately after doing the screen.

If they can do a baseline assessment: Based off of this screen, we would like to schedule you for the first of two lab assessments for the baseline visit. It should take about an hour to complete.

- Yes: Schedule first baseline assessment.

When scheduling initial visit, refer to the lab's Google calendar and make sure to schedule the family when a lab visit is available. If none of the times listed on the calendar work for the family, let them know that you will keep their contact information and call them to schedule a lab visit as soon as more days/times become available.

Double check that the child is within the age limit. Use the age calculator on the excel sheet to confirm when the child is 3 and 6 years old. Make sure to schedule the visit sometime after their 3rdbirthday or before their 6thbirthday.

*If child does not turn three for a few months, let them know we will call sometime in September to schedule the visit at that time.

- No: Ask if they would be interested in being sent more information about the study. Thank them for their time and mark requested more information.

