Interviewer: I just have a few questions about problems you may have had. For this phone screen we have to ask about a whole range of experiences. Some of these experiences are quite rare, but it would be great if you could bear with us and answer the questions I am going to ask you now.

- A. Has there been a time in your life when you had five or more drinks (beer, wine, or liquor) on one occasion?
 - a. Yes No
 - b. If yes, "Do you currently drink five or more drinks on any one occasion?
 - i. Yes No
- B. Have you ever used street drugs?
 - a. Yes No
 - b. If yes, "Do you currently use street drugs?
 - i. Yes No
- C. Have you ever gotten "hooked" on a prescribed medicine or taken a lot more of it than you were supposed to?
 - a. Yes No
 - b. If yes, "Are you currently hooked on a prescribed medicine?
 - i. Yes No
- D. Over the past year, have there been times when you felt extremely happy without a break for days on end?
 - a. Yes No
 - b. If yes, "Was there a reason for this?
 - i. Yes No
 - ii. If yes, what was the reason? _____
- E. Over the past year, have you ever felt that your thoughts were directly interfered with or controlled by some outside force or person?
 - a. Yes No
 - b. If yes, "Did this come about in a way that many people would find hard to believe, for instance, through telepathy?
 - i. Yes No
- F. Over the past year, have there been times when you felt that people were against you?
 - a. Yes No

b. If yes, "Have there been times when you felt people were deliberately acting to harm you or your interests?

i. Yes No

1. If yes, "Have there been times when you felt that a group of people was plotting to cause you serious harm or injury?"

a. Yes No

G. Over the past year, have there been times when you felt that something strange was going on?

a. Yes No

b. If yes, "Did you feel it was so strange that other people would find it very hard to believe?"

i. Yes No

H. Over the past year, have there been times when you heard or saw things that other people couldn't?

a. Yes No

b. If yes, "Did you at any time hear voices saying quite a few words or sentences when there was no one around that might account for it?"

i. Yes No

I. Have you ever wished you were dead or wished you could go to sleep and not wake up?

a. Yes No

b. If yes, "Did you have any of these thoughts in the past week, including today?"

i. Yes No

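### In the phone-screen suicide-risk ladder, past-week thoughts of method change the response only if urge or intention is also endorsed, so a parent with method thoughts but no stated intent is held to the lowest rung

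*Combined protocol and SAP*

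**What the plan says.** The instructions for section VI of the phone screen (item 8) set four triggers.

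- **First rung:** "Endorses first question of letter 'I': passive ideation". The interviewer is told "Complete the top section of the Suicide Risk Assessment Form (Assessment of Suicidal Thoughts" and tells the parent that the lead will be in touch within 24 hours.
- **Second rung:** "Endorses 'I' and '1': Strong Intent". The interviewer makes an in-depth assessment ("Fill out the entire Suicide Risk Assessment Form (1 page") and, having announced the lead's call, asks "How confident are you that you can keep yourself safe until then". A parent who is not confident is moved up: "Not able to keep themselves safe: go thru procedure for 'imminent risk' as seen below".
- **Third rung:** "Endorses 'I', '1' and '2': Imminent Risk". This requires the entire form, advice to seek help quickly, and hospital or 911.
- **Separate route, K(c):** a suicide attempt in the past week leads to the entire form whatever the answer to item 1.

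At every level the interviewer must call the lead straight after the screen.

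On the Phone Screening Form, section VI, the first question of I is a lifetime one: "Have you ever wished you were dead or wished you could go to sleep and not wake up". Part (b) asks whether such thoughts occurred in the past week. Item 1 asks about past-week urge and intention. Item 2 asks about past-week thoughts of method, then preparation, then means. The extracted text shows no rule on whether item 2 follows a no to item 1, and no Yes/No line for item 2.

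**The concern.** Item 2 is the only question under I about method, yet no trigger uses it without item 1. A parent who has thought in the past week about how to end their life, but denies a strong urge or intention, is placed by the written rule with a parent whose only endorsement is a wish to be dead at some time in life.

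At stake is what the interviewer must do while the parent is still on the line. The second rung treats the wait for the lead's call as something to be checked with the parent. The first rung carries the same 24-hour promise with no such check scripted. Section VI is reached only by parents with a PSI-4 Short Form raw score of 110 or higher, so the callers are selected for high parenting stress. A written ladder exists so that the response does not rest on the interviewer's judgement. Here it leaves one recognisable pattern to that judgement.

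**Working it through.** There is no planned figure to reproduce. The check is of the trigger logic and of the steps each trigger requires.

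**Inputs.** The triggers come from item 8 of the phone screen instructions: I; I and 1; I and 1 and 2; K(c). The content of the items comes from section VI of the Phone Screening Form.

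**Step 1: all answer patterns.** Four yes/no answers (I, 1, 2, K(c)) give 2 × 2 × 2 × 2 = 16 patterns, or 16 / 2 = 8 pairs that differ only in item 2. The table gives the highest rung reached.

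| I | 1 | K(c) | Item 2 = no | Item 2 = yes |
|---|---|---|---|---|
| no | no | no | none | none |
| no | no | yes | K(c) | K(c) |
| no | yes | no | none | none |
| no | yes | yes | K(c) | K(c) |
| yes | no | no | first | first |
| yes | no | yes | first + K(c) | first + K(c) |
| yes | yes | no | second | third |
| yes | yes | yes | second + K(c) | third + K(c) |

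Item 2 alters the response in 2 of 8 pairs, both with item 1 endorsed. In the 4 pairs (8 patterns) with item 1 denied, it alters nothing. The rows with I denied are included for completeness only.

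**Step 2: what the fifth row costs if item 2 is asked regardless.** Beyond the first rung, the second requires (a) the entire form in place of its top section and (b) the safety-confidence question with its branch to the imminent-risk procedure. That is 2 steps. For I and 2 without 1, and no past-week attempt, the ladder requires 0 of these 2.

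**Step 3: what happens if item 2 is asked only after a yes to item 1.** The fifth-row pattern with item 2 endorsed cannot then be observed. A parent who denies item 1 is asked 0 of item 2's 3 questions (method, preparation, means) in this sequence.

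**Step 4: what still happens on the first rung.** The top section of the risk form is completed, the parent is told of follow-up within 24 hours, and the lead is called as soon as the screen ends. The parent's location was taken earlier in the call, and interviewers are told to record details. The lead's involvement starts after the call with the parent, so it does not direct what is asked during that call.

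**The case against.** The strongest objection is that the Suicide Risk Assessment Form is not in the documents. Every first-rung parent gets its top section, whose title concerns suicidal thoughts, and questions on method or safety may sit there. This stands. A reader might infer that the call must miss method or safety for these parents however item 2 is handled. The documents do not support that; they show only what the ladder itself requires.

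Second, layout may have been lost in extraction, and some text ahead of the screening script was removed, so a skip rule may exist. That also stands, but a skip rule would settle which of the two situations applies. It would not add a trigger for I and 2 without 1.

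Third, the lead is called at once after any endorsement, and if item 2 was asked, its answers can inform that call. A reader might infer that these parents get no response, or simply wait 24 hours. Neither is right: 24 hours is the outer limit, and the lead can act sooner. What remains is the required conduct during the call.

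Fourth, escalating on method thoughts without intent is a clinical threshold, and the screening material carries an ethics-board approval stamp. A past-week attempt is behaviour, so K(c) is an imperfect analogy. It shows only that the ladder already allows the entire form without item 1. The objection rightly rules out calling this pattern strong intent. It does not explain why a disclosed method should draw no more from the script than a lifetime wish to be dead.

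Finally, a remedy must respect part (b) of question I, the form's own step from lifetime to past week. It must also deal with the pronoun in item 2, which has no clear referent once item 1 is denied. Both points are accepted.

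**Conclusion.** The point holds in limited form. As written, item 2 changes the response only together with item 1. If item 2 is asked of everyone, a parent with past-week method thoughts, no stated urge or intention and no past-week attempt meets only the first-rung trigger, and 2 second-rung steps are not required. If it is skipped after a no to item 1, 0 of its 3 questions are asked in this sequence.

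This rests on the visible trigger lines being complete. The practical effect also depends on the top section of the unseen risk form, and would shrink if that section asks about method or safety. The counts are of script steps per affected parent, not of risk. The documents give no frequency for the pattern and none is assumed. A reader might infer a weakness in the trial's design or analysis; nothing here touches endpoints, sample size or any statistical figure. It is a low-cost participant-safety improvement that should be made.

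**What to change.** Make two changes before the form is next used.

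1. **Phone Screening Form, section VI, question I.** State that item 2 is asked whenever past-week thoughts are reported at I(b), whatever the answer to item 1, and still after a yes to item 1. Replace the pronoun with explicit wording, for example 'how you might end your life'. Add a Yes/No line if the original form has none, so that the ladder can use the answer.
2. **Phone screen instructions, item 8.** Add a trigger for I with 2 but without 1. It requires at minimum the entire one-page form and the safety-confidence question with its branch to the imminent-risk procedure. The clinical lead should choose a label that does not call this strong intent. Keep I, 1 and 2 together as imminent risk.

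With these changes, a parent who reports past-week thoughts and denies item 1 is asked all 3 of item 2's questions, and a yes brings 2 of the 2 missing steps. While editing, the lead should check what the top section of the risk form already asks, to avoid duplication.

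The cost is a few added lines of script, a few more one-page assessments by phone, and any ethics-board notice the site requires for a script change.
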